## ***Template Instructions***

### ***Sections that do not apply:***

- *In several sections, the addition of checkboxes for **Not Applicable** have been added to the template as responses.*
  - *If an N/A checkbox is present, select the appropriate justification from the list.*
  - *If an N/A checkbox is not present, or if none of the existing checkboxes apply to your study, you must write in your own justification.*
- *In addition:*
  - *For research where the only study procedures are records/chart review: Sections 19, 20, 22, 23, 24, 25, 31, and 32 do not apply.*
  - *For exempt research: Sections 31 and 32 do not apply.*

### ***Studies with multiple participant groups:***

- *If this study involves multiple participant groups (e.g. parents and children), provide information in applicable sections for each participant group. Clearly label responses when they differ. For example:*

**Response:**

**Intervention Group:**

**Control Group:**

### ***Formatting:***

- *Do not remove template instructions or section headings when they do not apply to your study.*

*If you are pasting information from other documents using the “Merge Formatting” Paste option will maintain the formatting of the response boxes.*

### ***Amendments:***

- *When making modifications or revisions to this and other documents, use the **Track Changes** function in Microsoft Word.*
- *Update the version date or number **on Page 3**.*

**March 02, 2022**

## GRANT APPLICABILITY:

*Indicate whether this protocol is funded by a grant (e.g. NIH, foundation grant). For a grant with multiple aims, indicate which aims are covered by this research proposal.*

*NOTE: This question does not apply to studies funded by a sponsor contract.*

*Include a copy of the grant proposal with your submission.*

Response: **Funding by Sunstar has ended; this is now an unfunded study.**

## RESEARCH REPOSITORY:

*Indicate where the research files will be kept, including when the study has been closed. The repository should include, at minimum, copies of IRB correspondence (approval, determination letters) as well as signed consent documents. This documentation should be maintained for 3 years after the study has been closed.*

**Response:** Study documents will be kept in the Periodontal Disease Research Center (PDRC), Foster Hall, UB South Campus and include clinical records and Informed Consents.

**Location:** UB South Campus, PDRC, Foster Hall

**Address:** [name]

**Department:** Oral Biology

## 1.0 Objectives

*1.1 Describe the purpose, specific aims, or objectives of this research.*

**Response:** Our main goal is to evaluate the efficacy of Supportive Periodontal Therapy (SPT), 0.12 % Chlorhexidine gluconate rinse (Paroex®) and Soft-Picks, after professional Scaling and Root Planing (SRP) on clinical, microbiological and immunological status in subjects with type 2 diabetes. Our second goal is to compare the response to periodontal therapy (SRP only versus SRP + SPT) in participants with and without diabetes. A clear understanding of how periodontal therapy affects clinical status and the microbiome could help to develop an effective treatment regimen for each subject.

*1.2 State the hypotheses to be tested, if applicable.*

*NOTE: A hypothesis is a specific, testable prediction about what you expect to happen in your study that corresponds with your above listed objectives.*

**Response:**

1. Supportive Periodontal Therapy (SPT) using Paroex® mouthrinse (0.12% chlorhexidine) and Soft-Picks leads to improved clinical status and change in oral microbiome greater than when Scaling and Root Planing (SRP) only is used.

2. There will be about 35% who will be “Poor Responders” (PRs) (those needing Rescue Therapy). The number of PRs in diabetics will be higher than in non-diabetics. Poor Responders will have different clinical and microbiome in characteristics than responders.

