### 3.0 Background

- 3.1 *Provide the scientific or scholarly background, rationale, and significance of the research based on the existing literature and how it will contribute to existing knowledge. Describe any gaps in current knowledge. Include relevant preliminary findings or prior research by the investigator.*

*Response:*

**Type 2 diabetes mellitus is a metabolic disease with high blood glucose levels due to either low or lacking insulin production or failure to properly respond to insulin. Diabetes affects more than 400 million people world-wide and the number is increasing each year. Continuously high blood glucose levels lead to many complications, for example, retinopathy, nephropathy, neuropathy, and cardiovascular disease. Complications of diabetes lead to significant morbidity and mortality as well as to a decrease in quality of life (QOL).**

**Diabetes and periodontal disease are also related and in a bidirectional manner. With poorly controlled blood glycemic levels,**

periodontal status is often aggravated, and severe periodontal conditions are associated with poorer glycemic control. Systematic reviews and meta analyses conclude that periodontal disease leads to 0.36% to 0.65% reductions in hemoglobin A1c (HbA1c). However, a multi-centered clinical trial showed non-surgical periodontal therapy did not improve glycemic control. Borgnakke et al reviewed the paper and found baseline HbA1c levels were already close to desired levels so there was little room for improvement. In addition, obesity could have influenced the results as it increases inflammation. A small percentage of patients even without diabetes do not respond well to SRP which could be related to poor home care, incomplete root planning and/or impaired or different host immune responses, or anatomic structures that preclude healing after therapy such as furcation clefts, enamel projections or other root abnormalities. Columbo et al found distinctly different microbial profiles in those who did not respond well to periodontal therapy by using the Human Oral Microbe Identification Microarray in comparison to those who did.

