**Group A: Diabetic, Scaling & Root Planing (SRP) + Paroex® + Soft-Picks**

**Group B: Non-Diabetic, SRP + Paroex® + Soft-Picks**

**Group C: Diabetic, SRP**

**Group D: Non-Diabetic, SRP**

## 5.0 Local Number of Subjects

5.1 *Indicate the total number of subjects that will be enrolled or records that will be reviewed locally.*

Response: **104 with complete data; 26 per group**

5.2 *If applicable, indicate how many subjects you expect to screen to reach your target sample (i.e. your screen failure rate).*

Response: **250**

5.3 *Justify the feasibility of recruiting the proposed number of eligible subjects within the anticipated recruitment period. For example, how many potential subjects do you have access to? What percentage of those potential subjects do you need to recruit?*

Response: **We have a list of participants in previous studies that have given us permission to re-contact them about new studies. We also have a successful history of being able to make and surpass recruitment goals. Tactics such as word of mouth, flyers and posters, and ads have worked well in the past.**

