## 6.0 Inclusion and Exclusion Criteria

6.1 *Describe the criteria that define who will be **included** in your final study sample.*

*NOTE: This may be done in bullet point fashion.*

**Response: Inclusion Criteria:** To be in this study subjects must meet all of the following criteria:

- 1) Be able to understand the informed consent form and be willing and able to read and sign it.
- 2) At least 25 years of age.
- 3) Be able to understand and follow directions for study procedures.
- 4) At least 14 natural teeth, not counting third molars (“wisdom teeth”).
- 5) For moderate periodontal disease: At least four (4) teeth with at least one (1) site with  $\geq 5$  mm pocket depth (PD) and at least two (2) of the affected teeth with  $\geq 2$  mm alveolar bone loss as shown on radiographs. For Severe periodontal disease: At least eight (8) teeth with at least one (1) site with  $\geq 5$  mm pocket depth (PD) and at least two (2) of the affected teeth with  $\geq 2$  mm alveolar bone loss as shown on radiographs.

6.2 *Describe the criteria that define who will be **excluded** from your final study sample.*

*NOTE: This may be done in bullet point fashion.*

**Response: Exclusion Criteria:** Presence of the following criteria results in ineligibility for this study;

- 1) Presence of orthodontic appliances (“braces”).
- 2) An abnormal condition of lips, lining of the mouth, tongue, or gums (except for periodontal disease). If subject has a cold sore, canker sore, or injury in their mouth, they may return after the sore or injury heals.
- 3) Abscess of the gingiva caused by periodontal disease, or visible gross tooth decay
- 4) A broken tooth root or an abscessed tooth, per clinician’s judgement. Subject may be allowed to participate in the study after the condition is successfully treated or the study dentist reviews the condition and does not feel it will jeopardize the results of the study.
- 5) Periodontal treatment in the past 6 months.
6. Antibiotic therapy in the past three (3) months.

- 7) Have used cigarettes or other tobacco products in the past year.
- 8) Body mass index (BMI) is  $> 45$ .
- 9) Have regularly used non-steroidal anti-inflammatory drugs (such as  $\geq 325$  mg aspirin or ibuprofen) over the past 3 weeks.
- 10) Regularly using drugs that weaken the immune system (such as corticosteroids taken by mouth or injection, and cyclosporine).
- 11) Have participated in another clinical research study in the past 30 days.

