**BASELINE VISIT:**

- 1. Review medical and dental histories.**
- 2. Baseline Taste Test**
- 3. Oral Health Examination:**
  - a) Plaque Index (PI)**
  - b) Probing Pocket Depth (PPD)**
  - c) Bleeding on Probing (BOP)**
  - d) Gingival Index (GI)**
  - e) Clinical Attachment Level (CAL)**
- 4. Collect samples:**
  - a) Blood (FBS, HbA1c, Insulin, hs-CRP and microbiome testing, and for future testing of C-peptide, proinsulin, total GLP-1, PYY,**

DPP-IV, glucagon, LPS, soluble-TNF $\alpha$  RI and RII, MGO, TMAO, creatinine, and for future unknown testing.

- b) Subgingival plaque and saliva.
- c) Fecal, skin, and vaginal samples

3. Treatment: All participants will receive full mouth SRP within one month of the baseline visit.

4. Oral health instruction: All participants will receive oral hygiene instruction from the hygienist.

5. Participants will be randomized into one of the four groups.

6. Groups A and B will receive the product, Soft-Picks, and information on how to use them.

7. Make an appointment for 3 months after Baseline Visit.

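### The diabetic versus non-diabetic comparison is not randomised, Poor Responder status depends on how much disease a participant starts with, and no adjustment for baseline severity is specified

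*Combined protocol and SAP*

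**What the plan says.** Section 1.1 sets the second objective: "Our second goal is to compare the response to periodontal therapy (SRP only versus SRP + SPT) in participants with and without diabetes". Section 1.2 makes it directional for Poor Responders, defined as those needing Rescue Therapy: "The number of PRs in diabetics will be higher than in non-diabetics". The only rate given is overall: "There will be about 35% who will be" Poor Responders.

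Diabetes status is built into the four groups listed in Section 4.1, for example "Group C: Diabetic, SRP". Section 10.1 (Baseline Visit) nevertheless states: "Participants will be randomized into one of the four groups". No stratification or matching factor is named. The planned size is 26 per group, so 52 diabetics and 52 non-diabetics.

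Inclusion criterion 5 (Section 6.1) admits moderate disease from four affected teeth. It adds a second class: "For Severe periodontal disease: At least eight (8) teeth with at least one (1) site with" a pocket of 5 mm or more. The severe class lies inside the moderate one, and neither class is used again.

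At the 6- and 9-month visits (Section 10.1), Rescue Therapy is tied to sites that are still at 5 mm or more or have deepened to that level, alongside wording that leaves the decision to the clinician.

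Section 17.1 limits the statistics to descriptive analyses and lists univariate comparisons by diabetes status and treatment group. Its one adjustment sentence plans multivariable logistic regression for other risk factors. That sentence directly follows one about identifying oral bacteria, and it names neither an outcome nor a covariate.

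**The concern.** Only SRP versus SRP+SPT can be randomised. Diabetics and non-diabetics are two recruited populations and may differ at entry in the extent of periodontal disease, age or BMI. Section 3.1 makes a difference in extent plausible: where glycaemia is poorly controlled, "periodontal status is often aggravated".

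This matters for Poor Responder status because the trigger is largely an absolute residual depth at individual sites. If every deep site heals equally well in both populations, the population with more deep sites still produces more participants with at least one site left at 5 mm or more. A raw comparison therefore mixes two statements: that diabetics respond less well, and that diabetics started with more disease. The 6-month PPD change by diabetes status has the same gap, since no baseline covariate is named for it. The documents give no basis for the direction or size of the effect there, so it is not quantified.

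The results are meant to feed a larger study, and an excess that reflects starting extent would be carried into its planning.

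**Working it through.** The plan states no expected difference, test or power for Poor Responders by diabetes status. Its 35% overall rate is the only figure to calibrate to, so the illustration is built to reproduce it. The sample-size calculation in Section 17.2 concerns PPD and does not bear on this point.

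**Inputs from the documents.** Overall Poor Responder rate 35% (Section 1.2); minimum of 4 affected teeth for the moderate class and 8 for the severe class (Section 6.1); 52 versus 52 participants (2 × 26, Section 5.1).

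**Assumptions.** One deep site per affected tooth, at the class minimum (4 or 8). Each site independently stays at 5 mm or more with probability q, the same with and without diabetes. One such site makes a Poor Responder. Half of all participants are in the severe class. The severe shares within each diabetes group are unknown and are varied.

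**Step 1, calibrate q.** With u = (1 − q)^4, the Poor Responder risk is 1 − u in the moderate class and 1 − u² in the severe class. Setting the average to 0.35:

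- u + u² = 1.3, so u = (−1 + √6.2)/2 = 0.745
- q = 1 − 0.745^(1/4) = 0.071
- moderate risk = 25.5%, severe risk = 44.5%, average 35.0%

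**Step 2, mix the classes.** With severe share a in diabetics and b in non-diabetics, the excess is (a − b) × (0.445 − 0.255) = (a − b) × 0.190. At 70/30, for example, diabetics have 0.7 × 0.445 + 0.3 × 0.255 = 38.8% and non-diabetics 0.3 × 0.445 + 0.7 × 0.255 = 31.2%.

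**Step 3, chance of a significant diabetic excess** in an unadjusted two-sided 5% test: Φ[(excess − 1.96 × SE0)/SE1]. SE0 = √(2 × 0.35 × 0.65/52) = 0.0935, and SE1 is the unpooled standard error.

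| Severe share, diabetic / non-diabetic | Poor Responders | Excess (points) | Chance of significant excess |
|---|---|---|---|
| 50 / 50 | 35.0% vs 35.0% | 0 | 2.5% |
| 60 / 40 | 36.9% vs 33.1% | 3.8 | 6.0% |
| 70 / 30 | 38.8% vs 31.2% | 7.6 | 12.5% |
| 80 / 20 | 40.7% vs 29.3% | 11.4 | 22.8% |
| 100 / 0 | 44.5% vs 25.5% | 19.0 | 52.9% |

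Correlation between sites within a mouth would shrink every excess in the table.

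**Step 4, does adjustment work?** In 20,000 simulated trials of 52 versus 52 with equal risk by diabetes status within each class, class risks were set at 25% and 45%. The unadjusted two-sided test was positive in 7.5% of trials at 60/40 and 14% at 70/30. With a steeper assumed gradient (15% and 55%) at 70/30, the excess was 16 points and the test was positive in 41%. A Cochran-Mantel-Haenszel test stratified by severity class was positive in 4.8% to 5.2% across all simulated scenarios, which ran from 50/50 to 70/30. This works fully because class carries all the severity risk in the simulation. With real data, a count of deep sites or mean depth is likely to capture more of it.

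**The case against.** Four arguments can be made for the plan as it stands.

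- **Severity may lie on the pathway.** If diabetes worsens periodontal status, an excess acting through severity is part of the total association, and Hypothesis 2 does not claim independence from severity. This stands. It is a reason to report both results, not a reason to omit the adjusted one.
- **The trigger is not mechanical.** The 3-month options include no additional treatment, and the later visits leave room for the clinician's decision. This also stands: the site-count model is a simplification. The rescue wording differs between the 3-month visit and the 6- and 9-month visits and must be reconciled, because it defines a Poor Responder. The later wording still rests largely on residual depth, so dependence on baseline extent remains.
- **Adjustment is already planned.** Section 17.1 does plan logistic regression, and Section 10.1 says the need for rescue will be considered in the analysis. Neither names baseline severity or says how Poor Responders will be compared.
- **It is a descriptive pilot.** That lowers the stakes. But Section 1.2 states a directional hypothesis, and a descriptive comparison of unlike groups misleads just as easily.

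A reader might also infer that diabetics in this trial are known to start with worse disease. The documents do not support that. Section 3.1 speaks of poorly controlled glycaemia in general, there is no glycaemic entry criterion, and both populations face the same periodontal criteria.

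**Conclusion.** The point holds as a gap in the analysis plan. The diabetes comparison is observational, its clinical outcome depends on starting extent, and no adjustment for baseline severity is specified for Poor Responders or for PPD change. The randomised comparison of SRP with SRP+SPT within each diabetes group is not affected.

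The size is conditional. Under the stated assumptions, a spurious excess of about 4 to 11 points goes with severe shares from 60/40 to 80/20. About 19 points needs complete segregation of the classes. The actual imbalance is not in the documents.

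A reader might infer a larger excess, of 15 to 24 points, by comparing one participant at the four-site minimum with one at the eight-site minimum. For site failure of 5%, 10% and 20% the risks are 19% vs 34%, 34% vs 57% and 59% vs 83%. The documents do not support that as an expected bias. It puts every diabetic at the severe minimum and every non-diabetic at the moderate minimum. At an even mix, the 10% and 20% cases also imply overall rates of about 46% and 71%, not the protocol's 35%.

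**What to change.** In Section 17.1:

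1. State that the comparison by diabetes status is an observational association and that only SRP versus SRP+SPT is randomised. Reword the Baseline Visit item in Section 10.1 to match.
2. Report the diabetic versus non-diabetic comparison of Poor Responders and of 6-month PPD change twice: unadjusted, and adjusted for baseline severity (number of sites with PPD at or above 5 mm, or baseline mean PPD), age and BMI.
3. Say what each result answers. The adjusted one describes response at equal starting severity; the unadjusted one describes the overall association with diabetes.

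Stratifying treatment allocation by severity class would not help here. It balances SRP against SRP+SPT and leaves any severity difference between diabetics and non-diabetics untouched.

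The cost is a few sentences and a few degrees of freedom. Baseline PPD is recorded at the Baseline Visit, and date of birth, height and weight at screening, so no new data are needed.

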## 2.0 Scientific Endpoints

*2.1 Describe the scientific endpoint(s), the main result or occurrence under study.*

*NOTE: Scientific endpoints are outcomes defined before the study begins to determine whether the objectives of the study have been met and to draw conclusions from the data. Include primary and secondary endpoints. Some example endpoints are: reduction of symptoms, improvement in quality of life, or survival. Your response should **not** be a date.*

1. *Response:* Primary endpoints;

**Primary Endpoints:**

1. **Change in Probing pocket depth (PPD) at the 6-month post-SRP completed at Baseline.**

**Secondary Endpoints:**

1. **Oral clinical variables:** Changes in Bleeding on Probing (BOP), Clinical attachment level (CAL), and Gingival Index and Plaque Index (PI) at 3, 6, 9, and 12 months after treatment (Baseline); Change in PPD at 3, 9, and 12 months after treatment.
2. **Systemic variables:** Changes in Hemoglobin A1c (HbA1c); Fasting blood glucose (FBG); Immunoreactive insulin (IRI); High sensitivity C-reactive protein (hs-CRP); at 3, 6, and 12 months after treatment. Blood for C-peptide; proinsulin; total GLP-1, PYY, dipeptidyl peptidase-IV (DPP-IV); glucagon; plasma endotoxin (LPS); soluble TNF- $\alpha$  RI and RII; the dicarbonyl methylglyoxal (MGO), and Trimethylamine-N-Oxide (TMAO) will be collected at 3, 6, and 12 months study visits, but tested later.
3. **Microbiology endpoints:** Changes in Subgingival salivary and gut microbiome after periodontal treatment (SRP or SRP + SPT). Changes in the skin and vaginal microbiome after treatment will be assessed as resources permit.

### 3.0 Background

- 3.1 *Provide the scientific or scholarly background, rationale, and significance of the research based on the existing literature and how it will contribute to existing knowledge. Describe any gaps in current knowledge. Include relevant preliminary findings or prior research by the investigator.*

*Response:*

**Type 2 diabetes mellitus is a metabolic disease with high blood glucose levels due to either low or lacking insulin production or failure to properly respond to insulin. Diabetes affects more than 400 million people world-wide and the number is increasing each year. Continuously high blood glucose levels lead to many complications, for example, retinopathy, nephropathy, neuropathy, and cardiovascular disease. Complications of diabetes lead to significant morbidity and mortality as well as to a decrease in quality of life (QOL).**

**Diabetes and periodontal disease are also related and in a bidirectional manner. With poorly controlled blood glycemic levels,**

periodontal status is often aggravated, and severe periodontal conditions are associated with poorer glycemic control. Systematic reviews and meta analyses conclude that periodontal disease leads to 0.36% to 0.65% reductions in hemoglobin A1c (HbA1c). However, a multi-centered clinical trial showed non-surgical periodontal therapy did not improve glycemic control. Borgnakke et al reviewed the paper and found baseline HbA1c levels were already close to desired levels so there was little room for improvement. In addition, obesity could have influenced the results as it increases inflammation. A small percentage of patients even without diabetes do not respond well to SRP which could be related to poor home care, incomplete root planning and/or impaired or different host immune responses, or anatomic structures that preclude healing after therapy such as furcation clefts, enamel projections or other root abnormalities. Columbo et al found distinctly different microbial profiles in those who did not respond well to periodontal therapy by using the Human Oral Microbe Identification Microarray in comparison to those who did.

In the past decade, the development of new next generation sequencing (NGS) techniques have shown a greater number of organisms that are related to periodontal disease than previously found when older assessment techniques were used. These older measures (for example, culturing) limited the number of bacteria that could be identified at one time and likely led to an incomplete understanding of the association between periodontal disease and diabetes. NGS allows for the characterization of hundreds of oral bacteria rather than a few leading to a more comprehensive assessment of the oral microbiome than was previously possible. The more complete assessment increases our ability to more fully examine the association between subjects with and without periodontal disease, those with and without diabetes and those with periodontal disease and diabetes versus those without either. Genco et al found correlations between periodontal status and the subgingival microbiome in diabetics; however, periodontal status has stronger correlations with subgingival microbiome composition than diabetes. In a pilot study, *Anaeroglobus* and *Parvimonas* are more abundant in subjects with diabetes and periodontitis compared to those without diabetes but with periodontitis and those bacteria may be newly discovered periodontal pathogens.

There are few published reports investigating the efficacy of periodontal therapy on the microbiome in diabetics. We hypothesize that the microbiome influences clinical response to periodontal therapy and systemic changes showing improvement in diabetes status, i.e., improvement in HbA1c. As an adjunct to the professional mechanical periodontal therapy, chlorhexidine gluconate rinse previously demonstrated significant clinical improvements especially the reduction of bleeding, gingival inflammation, and dental

plaque accumulation. Moreover, interdental tooth cleaners removed more dental plaque effectively than only brushing and was followed by a reduction in gingival inflammation. Therefore we developed the plan to add SRP or SRP + SPT to the non-diabetic groups to determine the differences in response between diabetics and non-diabetics. The main aim of this study is to evaluate the effects of Supportive Periodontal Therapy, 0.12 % Chlorhexidine gluconate rinse (Paroex®) and a rubber interdental bristle cleaner (Soft-Picks) after professional Scaling and Root Planning (SRP), on clinical, microbiological and immunological status of subjects with type 2 diabetes and periodontal disease. The second aim is to compare the response to Supportive Periodontal Therapy, SRP alone or SRP+SRP, between patients with and without type 2 diabetes. A clearer understanding of how periodontal therapy affects diabetes status could lead to the development of novel new targeted approaches to therapy of both periodontal disease and diabetes.

